3.9.3 Indirect comparison

For CRAD001M2305 patients, all data described below will be pooled with the corresponding data from Study CRAD001M2301.

If the missing data pattern is not limiting and if the number of patients in each study is sufficient, an indirect comparison between patients treated by everolimus (from CRAD001M2305 study) and those who never received an mTOR inhibitor (TOSCA subset of patients) will be performed to evaluate the everolimus effect on growth and sexual development. Due to the observational nature of the TOSCA registry and its limited duration of follow-up, the statistical analysis will be primarily descriptive.

The following steps will be followed:

- The following non-exhaustive list of baseline characteristics will be used to assess potential imbalances between the two groups of patients: age at baseline, race, country, gender, age at first diagnosis of TSC, height abnormality at baseline, BMI abnormality at baseline, TSC mutation, type of TSC lesions, endocrine abnormality at baseline, Tanner Stage at baseline.
- If any imbalances that are deemed to affect the comparison of the two groups are identified in the step above, propensity scores will be calculated using the appropriate statistical model according to the observed missing data pattern. The propensity score is the conditional probability of being a member of one of the groups to be compared (i.e. probability of being from the CRAD001M2305 study) given the patient's covariates [D'Agostino 1998, Rosenbaum 1984].
- Strata defined by the propensity scores (e.g. quintiles) will be then created and the balance between the groups within those strata will be examined.
- If deemed relevant, the estimated propensity scores may then be used to obtain estimates for the effect of everolimus on growth (respectively sexual) development, through matching and/or logistic regression adjustment, using the CRAD001M2305 and TOSCA FAS (respectively FAS Puberty) analysis sets. Matching will be considered if there is a much larger sample size of untreated (TOSCA) patients as compared to the CRAD001M2305 patients. In regression adjustment the propensity score may be included either as its raw score or as per the defined strata. In addition to the propensity score a subset of the other baseline characteristics covariates may be included.

The following should be noted: the above described use of propensity scores is exploratory and highly dependent on the observed data (observed imbalances between groups, observed missingness pattern) and therefore it is not possible to fully pre-specify all aspects of the planned analyses. In addition, whereas a formal randomization guarantees that there should be no systematic differences in observed and unobserved covariates between the groups to be

compared, the propensity scores are conditional only on the observed covariates. Thus, even if the use of propensity scores is intended to reduce bias and increase precision of the treatment effect, these indirect comparisons analyses using the propensity score methodology will be considered exploratory only and should be interpreted with cautious.

For each covariate used to investigate the imbalances between the two groups (and then calculate the propensity score) the missing-data mechanism will be explored. If relevant (depending on the number of patients in the TOSCA Full Analysis Sets, amount of missing data, missing-data mechanism), specific methods like Multiple Imputation or ECM algorithms may be considered to estimate the propensity scores in presence of missing data. Handling of missing data is an evolving field of research and additional methods may be considered at the time of the availability of these long-term data.

If the missing data pattern is not limiting, the effect of everolimus on height (respectively BMI) growth abnormality may also be assessed as an exploratory analysis through the use of propensity scores in a logistic regression or matching comparison as detailed before. The same analysis will be performed for the achievement of Tanner Stage V by age 16 (for females) or age 17 (for males).

3.10 Pharmacokinetic analyses

The pharmacokinetic (PK) analyses will be described only for CRAD001M2305 patients under the safety set.

Blood trough levels collected at investigator discretion in compliance with local product information should be recorded, if available.

The time-normalized C_{min} value will be estimated for the treatment period using recorded everolimus C_{min} values and prescribed doses in that treatment period. C_{min} will be summarized with descriptive statistics over time in the SS.

Time-normalized C_{min} (C_{min,TN}) will be calculated over each assessment interval (t₁, t₂). The time-normalized C_{min} is defined as:

$$C_{min,TN} = (C_{min,t1} * p1 + C_{min,t2} * p2) / (p1 + p2)$$

- C_{min} is considered to be the same within the same dosing interval (C_{min,ti} is the mean C_{mins} if multiple C_{mins} are available within a dosing interval)
- The dosing interval P_i is number of days in which the patient is treated with the same dose (in mg).
- If there is no valid C_{min} value available within a dose interval, the following imputation rule will be applied: the last C_{min,ti} value will be taken and multiplied by the ratio of the dose given in the current dose interval to that of the previous dose interval.
- The dose refers to the prescribed dose.

If a high rate of growth/puberty abnormalities occurs and if the number of CRAD001M2305 patients is sufficient, the potential relationships between C_{min} and growth/puberty data will be explored in the Safety Set as follow:

If the number of CRAD001M2305 patients is sufficient, the percentage of patients who will have reached Tanner Stage V by age 16 (for females) or age 17 (for males) will be presented

split by exposure to everolimus, in terms of patient's time-normalized C_{min}. As per everolimus label, the target C_{min} for pediatric patients is between 5 to 15 ng/mL, the time-normalized C_{min} will be categorized as < 5 ng/ml, 5-10 ng/ml and > 10 ng/ml. Note: if there are insufficient numbers of patients in one of the groups, the categories may be collapsed or redefined.

The same descriptive analyses will be performed for the rates of potential delayed puberty and for rate of notably low BMI/height SDS, if a high rate of growth/puberty abnormalities occurs and if the number of CRAD001M2305 patients is sufficient.

Pooled data will be listed.

3.11 Interim analysis

No formal interim analysis is planned for this study. However, safety outputs may be generated for regulatory safety updates.

3.12 Subgroup analysis

For the CRAD001M2305 patients, if the number of patients is sufficient, the following subgroups by duration of everolimus exposure will be used for some analyses:

- Less than 5 years of everolimus exposure (< 5 years)
- Between 5 years and 10 years of everolimus exposure (≥ 5 years - < 10 years)
- Ten years or more of everolimus exposure (≥ 10 years)

Note: if there are insufficient numbers of patients in one of the groups the categories may be collapsed or redefined.

3.13 Sample size calculation

No formal sample size calculation has been performed in this non-comparative study which consists in the long-term safety follow-up of CRAD001M2301 pediatric patients. It is anticipated that approximately 50 patients who have participated in CRAD001M2301 would be eligible to enter CRAD001M2305.

Based on the safety findings in Study CRAD001M2301 in terms of growth development where the estimated rate of patients with growth development abnormality was between 5 – 10% as of 11-Jan-2013 cutoff, it can be expected that the proportion of patients with growth development abnormality in this study would be in the same range, between 5 - 10%. The growth development abnormality would be defined as rate of notably low height SDS at the cut-off date of the analysis.

The proposed sample size of 50 patients will allow estimating a two-sided 95% confidence interval for rate of patients with growth development abnormality. [Table 3-1](#) below shows the exact binomial 95% confidence interval [[Clopper and Pearson 1934](#)] and the precision of the estimate for N=50 for various numbers of observed patients with growth abnormality. Note that the final interval will depend on the final sample size.

Table 3-1 95% confidence interval for different number of observed patients with growth development abnormality during CRAD001M2305 (sample size N = 50)

Number of patients with growth development abnormality	Rate of patients with growth development abnormality	Exact binomial 95% confidence interval
0	0.00	(0.00, 0.07)
2	0.04	(0.00, 0.14)
4	0.08	(0.02, 0.19)
6	0.12	(0.04, 0.24)
8	0.16	(0.07, 0.29)
10	0.20	(0.10, 0.34)
12	0.24	(0.13, 0.38)
14	0.28	(0.16, 0.42)

With this sample size of 50, if we observe 4 patients with growth development abnormality (which corresponds to an observed 8% rate) there will be 79% probability of true rate of patients with growth development abnormality $\leq 10\%$. Probabilities that the true rate of patients with growth development abnormality is lower or equal to 10% with different number of observed patients with development abnormality are illustrated in Table 3-2. These calculations are based on the binomial distribution.

Table 3-2 Probability that the true rate of patients with growth development abnormality is lower or equal to 0.10 as a function of number of observed patients with development abnormality

Number of observed patients with growth development delay	Observed rate of patients with growth development delay	P(true rate of patients with growth development delay ≤ 0.10 observed rate)
0	0.00	1.00
2	0.04	0.99
3	0.06	0.92
4	0.08	0.79
5	0.10	0.62
6	0.12	0.44
8	0.16	0.17
10	0.20	0.05

No power calculation was made for secondary analyses.

4 Change to protocol specified analyses

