4.2 Indirect Comparison Analysis

Confidence interval was so wide even for 1 patient with growth development abnormality as shown below in the table 1-1. Estimation was not robust due to the small sample size. Sample size of 15 patients is too small for any comparison, Considering the unlikelihood of making a robust analysis with the limited enrolment into CRAD001M2305, indirect comparison is not meaningful.

Table 1-1 95% confidence interval for different number of observed patients with growth development abnormality during M2305

Number of patients with growth development abnormality	Sample size N = 50		Sample size N = 15	
	Rate of patients with growth development abnormality	Exact binomial 95% confidence interval	Rate of patients with growth development abnormality	Exact binomial 95% confidence interval
0	0.00	(0.00, 0.07)	0.00	(0.00, 0.22)
1			0.07	(0.00, 0.32)
2	0.04	(0.00, 0.14)	0.13	(0.02, 0.40)
3			0.20	(0.04, 0.48)
4	0.08	(0.02, 0.19)	0.27	(0.08, 0.55)
5			0.33	(0.12, 0.62)
6	0.12	(0.04, 0.24)	0.40	(0.16, 0.68)
7			0.47	(0.21, 0.73)
8	0.16	(0.07, 0.29)	0.53	(0.27, 0.79)
9			0.60	(0.32, 0.84)
10	0.20	(0.10, 0.34)	0.67	(0.38, 0.88)
11			0.73	(0.45, 0.92)
12	0.24	(0.13, 0.38)	0.80	(0.52, 0.96)
13			0.87	(0.60, 0.98)
14				
	0.28	(0.16, 0.42)	0.93	(0.68, 0.998)

5 Appendix

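### SAP 3.13 still states the precision of the growth-abnormality rate for 50 patients, although SAP 4.2 gives the sample size as 15, where the lowest attainable 95% upper limit is about 22%

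*SAP*

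**What the plan says.** SAP 3.13 repeats protocol 10.8. It says that no formal sample size calculation was done and starts from an expectation: "It is anticipated that approximately 50 patients who have participated in CRAD001M2301 would be eligible to enter CRAD001M2305". It expects 5 to 10% of patients to have a growth abnormality, defined as notably low height SDS. It then states: "The proposed sample size of 50 patients will allow estimating a two-sided 95% confidence interval for rate of patients with growth development abnormality". Table 3-1 gives exact intervals for 50 patients. Of 4 events in 50, the section says "there will be 79% probability of true rate of patients with growth development abnormality" at or below 10%, and Table 3-2 extends that figure to other counts. There is one caveat: "Note that the final interval will depend on the final sample size".

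SAP 4.2, under changes to the protocol-specified analyses, says: "Sample size of 15 patients is too small for any comparison". It prints exact intervals for 15 patients beside those for 50, calls the estimation not robust, and concludes: "Considering the unlikelihood of making a robust analysis with the limited enrolment into CRAD001M2305, indirect comparison is not meaningful".

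The SAP's document history lists no change to 3.13. Section 4 records changes only to the pharmacokinetic analysis and the indirect comparison.

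**The concern.** One document carries two sample sizes for the same rate. The smaller, actual size is applied to a secondary comparison. The section that states the precision of the growth-abnormality rate, which SAP 3.8.1 reports under the primary objective, stays at the planned size.

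The protocol (2.1) describes this as a post-authorisation safety study done at the EMA's request, so a statement about a 10% rate is one that readers would look to for reassurance. Someone who reads 3.13 alone would take a result with no cases to carry an upper limit of 7%. The limit for 15 patients is 22%. The 79% figure and Table 3-2 have no counterpart for 15 patients anywhere in the SAP.

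**Working it through.** **Inputs.** Planned size 50, reference rate 10%, expected rate 5 to 10%, two-sided 95% level: SAP 3.13. Exact (Clopper-Pearson) interval: SAP 2.4.2.2. Actual size 15: SAP 4.2.

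**Step 1. Reproduce Table 3-1 (n = 50).** For x events in n, the lower limit is the 0.025 quantile of Beta(x, n−x+1) and the upper limit is the 0.975 quantile of Beta(x+1, n−x). With x = 0 the upper limit reduces to 1 − 0.025^(1/n).

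- 0/50: 1 − 0.025^(1/50) = 0.071 (printed 0.07)
- 4/50: 0.022 to 0.192 (printed 0.02 to 0.19)
- 10/50: 0.100 to 0.337 (printed 0.10 to 0.34)

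The printed limits agree with one trivial exception: the 6/50 lower limit is 0.0453, which rounds to 0.05 but is printed as 0.04.

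**Step 2. Reproduce Table 3-2 (n = 50).** Every row is obtained as P(X ≤ 5) for X ~ Binomial(50, x/50), where 5 is 10% of 50. For x = 2, 3, 4, 5, 6, 8 and 10 this gives 0.99, 0.92, 0.79, 0.62, 0.44, 0.17 and 0.05, as printed. So the 79% is the chance of at most 5 events in 50 if the true rate is 8%. It is not the probability that the true rate is at most 10% given 4/50. A calculation of that kind gives 0.59 with a uniform prior or 0.66 with a Jeffreys prior.

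**Step 3. The same interval at n = 15.**

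| Events | Exact 95% interval, n = 15 | Printed in SAP 4.2 |
|---|---|---|
| 0 | 0 to 0.218 | 0.00, 0.22 |
| 1 | 0.002 to 0.320 | 0.00, 0.32 |
| 2 | 0.017 to 0.405 | 0.02, 0.40 |

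The upper limit rises with every further event, so 0.218 is the minimum. Other methods at 0/15 also stay above 10%: one-sided 95% exact 1 − 0.05^(1/15) = 0.181, Wilson 0.204, Jeffreys 0.152.

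**Step 4. Size needed with no events.** Solve 1 − 0.025^(1/n) ≤ 0.10, that is n ≥ ln(0.025)/ln(0.90) = 35.01, so n = 36.

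**Step 5. The same test at n = 50.** 0/50 gives 0.071 and passes. 1/50 gives 0.1065 and fails. Only 0/50 passes. Its probability is 0.95^50 = 0.077 at a true rate of 5% and 0.90^50 = 0.005 at 10%.

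**Step 6. What no cases in 15 would mean.** The chance of 0/15 is 0.90^15 = 0.206 at a true rate of 10% and 0.95^15 = 0.463 at 5%.

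**Step 7. Would recomputing Table 3-2 help?** 10% of 15 is 1.5, so the analogue is P(X ≤ 1) for X ~ Binomial(15, x/15). For x = 0, 1, 2 and 3 it gives 1.00, 0.74, 0.39 and 0.17. The first row would print a probability of 1.00 next to an exact upper limit of 21.8%.

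**The case against.** The strongest reply is that nothing is hidden. Section 4.2 prints the 15-patient intervals for this same rate, including 0/15, and calls the estimation not robust. Section 3.13 is worded as planning and ties the 79% to 4 events in 50. It warns that the interval will change with the final size, and the reported intervals will be calculated from the data in any case. On this view only a cross-reference is missing.

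Much of that stands. A reader might infer that the SAP conceals its true precision; 4.2 shows that it does not. A reader might also infer that the study has lost the ability to meet a 10% criterion. The documents set no such criterion: SAP 2.4.2.1 plans no tests on rates, 10% is the top of an expected range and the reference value in an illustrative table, and the 50-patient plan would rarely have met it (Step 5). Nor is it a contradiction that an observed 8% cannot occur among 15 patients, since that example is stated for 50.

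The reply does not cover everything. The caveat in 3.13 concerns the interval, not the 79% sentence or Table 3-2. The actual size was already known when the amendment was released. The correct intervals appear only under a different analysis, and 3.13 does not point to them.

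**Conclusion.** The point holds as a defect of un-updated text: SAP 3.13 states a size and precision that the study, on the SAP's own account, does not deliver. For a result with no events, the upper limit shown is 7%, against 21.8% at 15 patients. No result at 15 can put the two-sided 95% upper limit at or below 10%. This is not an arithmetic error in the intervals and not a failed success criterion. It also does not change any planned analysis.

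The figures assume that all 15 patients contribute a height to the rate; with fewer, the lowest attainable upper limit is higher. They use the SAP's exact method, but the conclusion at 0/15 is the same with the other interval methods tried.

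**What to change.** In SAP 3.13:

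- Label 50 patients as the original planning assumption and state that the sample size is 15.
- Use the 15-patient exact intervals from 4.2 for the growth-abnormality rate, or cross-refer to them.
- State that the lowest attainable exact two-sided 95% upper limit is about 22% (0/15), so the study cannot place that limit at or below 10%.
- Delete the 79% sentence and Table 3-2. Do not recompute the table for 15 patients, since that would carry over a quantity that is not a probability about the true rate.

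In SAP Section 4, record that the precision statement for the growth-abnormality rate has changed, as well as the indirect comparison.

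The cost is wording only: no data, endpoint or analysis changes. The drawback for the sponsor is a less favourable stated precision.

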4.1 Pharmacokinetics data

PK data were collected using central lab for parent study CRAD001M2301 however local lab used for study CRAD001M2305. The local lab test processes are not validated by Sponsor, and it is varying among the local labs so the PK data from local lab are not comparable to the central

lab PK data available in CRAD001M2301. Therefore, PK analysis will be performed only on the data collected in CRAD001M2305 Study.

4.2 Indirect Comparison Analysis

Confidence interval was so wide even for 1 patient with growth development abnormality as shown below in the table 1-1. Estimation was not robust due to the small sample size. Sample size of 15 patients is too small for any comparison, Considering the unlikelihood of making a robust analysis with the limited enrolment into CRAD001M2305, indirect comparison is not meaningful.

Table 1-1 95% confidence interval for different number of observed patients with growth development abnormality during M2305

Number of patients with growth development abnormality	Sample size N = 50		Sample size N = 15	
	Rate of patients with growth development abnormality	Exact binomial 95% confidence interval	Rate of patients with growth development abnormality	Exact binomial 95% confidence interval
0	0.00	(0.00, 0.07)	0.00	(0.00, 0.22)
1			0.07	(0.00, 0.32)
2	0.04	(0.00, 0.14)	0.13	(0.02, 0.40)
3			0.20	(0.04, 0.48)
4	0.08	(0.02, 0.19)	0.27	(0.08, 0.55)
5			0.33	(0.12, 0.62)
6	0.12	(0.04, 0.24)	0.40	(0.16, 0.68)
7			0.47	(0.21, 0.73)
8	0.16	(0.07, 0.29)	0.53	(0.27, 0.79)
9			0.60	(0.32, 0.84)
10	0.20	(0.10, 0.34)	0.67	(0.38, 0.88)
11			0.73	(0.45, 0.92)
12	0.24	(0.13, 0.38)	0.80	(0.52, 0.96)
13			0.87	(0.60, 0.98)
14				
	0.28	(0.16, 0.42)	0.93	(0.68, 0.998)

5 Appendix

5.1 Imputation Rule

5.1.1 Study drug

The following rule should be used for the imputation of the dose end date for a given study treatment:

Scenario 1: If the dose end date is completely missing and there is no EOT page and no death date, the participant is considered as on-going:

The participant should be treated as on-going and the cut-off date should be used as the dose end date.

Scenario 2: If the dose end date is completely or partially missing and the EOT page is available:

Case 1: The dose end date is completely missing, and the EOT completion date is complete, then this latter date should be used.

Case 2: Only Year(yyyy) of the dose end date is available and yyyy < the year of EOT date:

Use Dec31yyyy

Case 3: Only Year(yyyy) of the dose end date is available and yyyy = the year of EOT date:

Use EOT date

Case 4: Both Year(yyyy) and Month (mm) are available for dose end date, and yyyy = the year of EOT date and mm < the month of EOT date:

Use last day of the Month (mm)

Case 5: Both Year(yyyy) and Month (mm) are available for dose end date, and yyyy = the year of EOT date and mm = the month of EOT date:

Use EOT date

All other cases should be considered as a data issue and should contact the data manager of the study.

After imputation, compare the imputed date with start date of treatment, if the imputed date is < start date of treatment:

Use the treatment start date

Participants with missing start dates are to be considered missing for all study treatment component related calculations and no imputation will be made. If start date is missing then end-date should not be imputed.

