## **7 Visit schedule and assessments**

### **7.1 Study flow and visit schedule**

[Table 7-1](#) lists all of the assessments and indicates with an “X”, the visits when they are performed. All data obtained from these assessments must be supported in the patient’s source documentation.

No CRF will be used as a source document.

	Day 1 / Enrollment	Every 3 months after Day 1 (3-monthly visits that coincide with the annual visits are skipped (every 4 th 3-monthly visit))			First annual visit	Every 3 months after each consecutive year (3-monthly visits that coincide with the annual visits are skipped (every 4 th 3-monthly visit))	Annually after first year	Study completion
Time Point (months)	0	3	6	9	12	15, 18, 21, 27...	24, 36...	Last
Visit No.	1	2	3	4	5	6, 7, 8, 10...	9, 13...	778
Visit Window		± 14 days			± 30 days	± 14 days	± 30 days	
Any available everolimus blood trough levels (C min ) as per label (D) (only while on everolimus treatment)	X	X	X	X	X	X	X	X
Prescribed everolimus dose (D) (only while on everolimus treatment)	X	X	X	X	X	X	X	X
Summary of dose interruptions (D) (only while on everolimus treatment)	X	X	X	X	X	X	X	X
Brain MRI scan dates (as available) (D)					X		X	
TAND Checklist (D)	X				X		X	
End of everolimus treatment (D)		X (as applicable, complete follow-up for safety 30-days after last dose)						

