### **7.1.3 Study completion**

Patients will meet the criteria for study completion upon demonstrating Tanner Stage V, or reaching age 16 (females) or age 17 (males), whichever comes first. Upon meeting the criteria for study completion, the patient should schedule an End of Study visit at the site. The End of Study visit cannot be completed via telephone contact.

Patients who discontinue commercial everolimus should continue study participation until meeting any of the aforementioned criteria for study completion. The discontinuation of everolimus will be recorded on the End of Treatment CRF page. Safety monitoring should be continued for at least 30 days following the last dose of everolimus.

Patients who complete the study, or discontinue the study early, should have the reason for exiting the study recorded on the Study Phase Completion Disposition CRF (SEC) page.

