2.2 Data included in the analysis

This Study CRAD001M2305 is a long-term safety follow-up study and statistical analyses will be primarily descriptive for all endpoints. The planned statistical analysis is described in Section 10 of the protocol.

Data collected for the patients enrolled in this CRAD001M2305 study will be pooled with the corresponding data previously collected in the parent CRAD001M2301 study for the same patients, in particular, background information on the disease history, demographics and baseline characteristics, everolimus exposure, sexual and growth development data. This pooling will allow for the following:

- Obtaining baseline values collected in CRAD001M2301 before start of everolimus
- Calculating the whole exposure to everolimus for patients enrolled in the CRAD001M2305 study
- Considering the whole growth/development course over time from the start of everolimus.

The descriptive analyses of data from the CRAD001M2305 study and TOSCA registry will be presented, side by side, whenever similar data are collected in both studies. This is intended to facilitate the interpretation of the CRAD001M2305 results and help describe any potential impact of everolimus on growth and sexual development, in the TSC population, whose growth and sexual development independent of exposure to systemic mTOR inhibitors is not well characterized.

Table 2-2 summarizes the data which will be included in all the analyses described in the SAP.

Table 2-2 Data included in each analysis

Endpoints	Studies			Analysis Set
	CRAD001M2305	CRAD001M2301	TOSCA	
Baseline characteristics	X	X	X	FAS and FAS Puberty
Patient disposition	X			FAS
Protocol deviations	X			FAS
Concomitant therapy	X	X		Safety Set
Height and BMI	X	X	X	FAS
Tanner stage	X	X	X	FAS puberty
Endocrines	X	X	X	FAS
Adverse events	X	X		Safety Set
Age at menarche	X	X		Safety Set
Age at thelarche	X	X		Safety Set
Age at adrenarche	X	X		Safety Set
Potential delayed puberty	X	X		Safety Set
TAND checklist	X		X	FAS
Indirect comparison	X	X	X	FAS and FAS puberty

Endpoints	Studies			Analysis Set
	CRAD001M2305	CRAD001M2301	TOSCA	
Treatment exposure	X	X		Safety Set
Pharmacokinetics	X	X		Safety Set

In order to ensure all data in the trial is captured, the cut-off date for final analysis will be fixed to the date of the last patient last visit. For the purpose of the final analysis, all tables, figures and listings (TFLs) described in this SAP as well as in TFL shells will be produced.

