If it is required to impute an end date in order to perform a specific analysis, the imputed date will be displayed and flagged in the listings. For example, if there is a record in the Everolimus prescription record panel with missing end date (or end date after the cut-off date), the cut-off date needs to be imputed as the end date in order to enable treatment exposure duration to be calculated.

Details of imputation of partial dates are provided in the programming specifications (Programming Dataset Specifications).

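### The SAP's dose-end imputation has no cap at the patient's own study exit, so an open everolimus record can run on to the study-wide last visit

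*SAP*

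**What the plan says.** SAP 5.1.1, Scenario 1, sets the condition: "If the dose end date is completely missing and there is no EOT page and no death date, the participant is considered as on-going". The consequence is "The participant should be treated as on-going and the cut-off date should be used as the dose end date". Scenario 2 covers patients who do have an EOT page; if the dose end date is completely missing, the EOT date is used.

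SAP 2.2 defines the cut-off: "the cut-off date for final analysis will be fixed to the date of the last patient last visit". It then gives its own example, a prescription record with no end date, for which "the cut-off date needs to be imputed as the end date in order to enable treatment exposure duration to be calculated". That example does not mention the EOT page.

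The protocol separates stopping the drug from leaving the study. On the first, Section 7.1.3 says "The discontinuation of everolimus will be recorded on the End of Treatment CRF page". On the second, patients who complete or leave early "should have the reason for exiting the study recorded on the Study Phase Completion Disposition CRF (SEC) page". In the visit schedule (Section 7.1), the row for end of everolimus treatment is qualified: "as applicable, complete follow-up for safety 30-days after last dose".

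**The concern.** A cut-off rule of this kind suits an interim data cut, when open records belong to patients still in follow-up. Here the cut-off is the end of the whole study. Each patient finishes at Tanner Stage V or at the age limit (16 for girls, 17 for boys), so by LPLV almost everyone has already left, some perhaps years before. Scenario 1 asks about the dose end date, the EOT page and death. It never asks whether the patient has left the study.

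Completers still on drug are foreseeable. Protocol 2.1 expects most patients to continue everolimus after M2301. The visit schedule collects the prescribed dose at the study completion visit for patients on treatment. SAP 3.5 counts patients started or ongoing on commercial drug separately from those who discontinued treatment.

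At stake are the exposure duration and cumulative dose tables, which are produced whatever the sample size. Also at stake is the assignment of patients to the exposure subgroups of SAP 3.12, starting with "Less than 5 years of everolimus exposure (< 5 years" and followed by 5 to under 10 years and 10 years or more. SAP 4.2 puts the sample at 15, so a few misdated records would visibly change these displays.

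**Working it through.** The plan states no exposure figure, so there is none to reproduce. The check has two parts.

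**1. Which end date applies to a completer on daily drug with an open record?**

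| Source | End date it gives |
|---|---|
| SAP 5.1.1 Scenario 1 (no EOT page, no death date) | LPLV |
| SAP 5.1.1 Scenario 2, Case 1 (EOT page exists) | EOT date |
| SAP 2.2 example (read literally, with or without an EOT page) | LPLV |
| SAP 5.1.2, Table 5-1, daily administration | Last non-zero dose; no rule if that date is missing |
| SAP 5.1.2, Table 5-1, period administration | Capped at last contact, but only for loss to follow-up (date of death for deaths) |
| Protocol 10.3 and SAP 3.6 | Commercial exposure reported in M2305 |

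No row caps the date at study completion. SAP 2.2 and Scenario 2 disagree when an EOT page exists. Both LPLV rows also disagree with Protocol 10.3 and SAP 3.6: time after exit is not reported in M2305, and Protocol 10.3 holds the prescribed dose constant only from one visit to the next.

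**2. Size per affected patient.**

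SAP 5.1.2: duration = last date − first date + 1.

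Excess = (LPLV − start + 1) − (exit − start + 1) = LPLV − exit.

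The start date cancels, so exposure in M2301 does not affect the excess. By SAP 5.1.3, the excess cumulative dose is the last recorded daily dose × (LPLV − exit) in days.

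The documents give neither exit dates nor the actual LPLV. Protocol 4.3 gives only September 2026 as the latest expected LPLV. Assumptions: start 1 July 2010; LPLV 30 September 2023, 30 June 2024 or 30 September 2026; no interruptions. Years = days / 365.25.

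| Own exit (30 June) | Ended at exit | LPLV Sep 2023 | LPLV Jun 2024 | LPLV Sep 2026 |
|---|---|---|---|---|
| 2016 | 6.00 | 13.25 (+7.25) | 14.00 (+8.00) | 16.25 (+10.25) |
| 2018 | 8.00 | 13.25 (+5.25) | 14.00 (+6.00) | 16.25 (+8.25) |
| 2020 | 10.00 | 13.25 (+3.25) | 14.00 (+4.00) | 16.25 (+6.25) |
| 2022 | 12.00 | 13.25 (+1.25) | 14.00 (+2.00) | 16.25 (+4.25) |
| 2023 | 13.00 | 13.25 (+0.25) | 14.00 (+1.00) | 16.25 (+3.25) |

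In this illustration, the 2016 and 2018 exits move from the 5 to under 10 year group to the 10-year-or-more group. The later exits stay in the top group. For exit in June 2018 and LPLV in June 2024, the excess is 2,192 days, each carrying the last recorded daily dose.

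**Upper end.** Protocol 5.3 excludes patients within 3 months of the age limit, so completion by age comes about 3 months after enrollment at the earliest. If that patient enrolled between mid-2014 and mid-2016 (assumed) and LPLV falls between September 2023 and September 2026 (assumed), the excess ranges from 7.0 to 12.0 years. For the last patient out it is zero.

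**The case against.** **The premise is conditional.** A reader might infer that every completer on everolimus lacks an EOT page and is therefore credited with years of extra exposure. The documents do not say so. The protocol says only what the EOT page records and that the end-of-treatment row applies where applicable. SAP 3.5 uses both the EOT and End of Study pages for its disposition counts, and SAP 2.1.6.1 describes growth data as collected until EOT, which may be a broader use of the term. The dose end date must also be completely missing. SAP 2.1.2 defines the last administration as a date recorded on the prescription record, and if that date is there, Scenario 1 never fires. This part of the objection stands: the point must be put as an *if*.

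**Other text confines exposure to study data.** Protocol 10.3 and SAP 3.6 count reported exposure, and SAP 5.1.3 ties actual cumulative dose to what is documented. That is true, but these passages do not override the explicit imputation rule. They show that the SAP needs reconciling.

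**The reach is limited.** Height and BMI scores, the Tanner Stage V percentage and the endocrine summaries do not use the dose end date. The exposure-outcome displays in SAP 3.8.1, 3.8.2 and 3.9.2 depend on sufficient numbers and mostly also on a high abnormality rate, and the SAP 3.12 subgroups may be collapsed. This stands too. The exposure tables carry no such condition.

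**Direction of bias.** Early leavers gain most, so a reader might infer a spurious link between longer exposure and faster maturation. That does not follow. With an open record and no interruptions, an affected patient's imputed total is prior exposure plus (LPLV − start of the M2305 record), in which the exit date does not appear. The net effect also depends on who is affected, which is unknown.

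**Conclusion.** The gap is real but conditional. If a patient completes or leaves M2305 on everolimus with no dose end date, no EOT page and no death date, the SAP credits exposure and cumulative dose up to the study-wide LPLV, including time after exit. SAP 2.2 read literally does this for any open record, in conflict with Scenario 2, and both rules conflict with Protocol 10.3 and SAP 3.6.

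The error per affected patient is exactly LPLV minus own exit: potentially years for early leavers, near zero for those leaving near LPLV. The figures in years rest on assumed dates. The number of affected patients, the average error, the share changing subgroup and the direction of any exposure-outcome bias cannot be determined from the documents, so no cohort average is given.

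This should be fixed, with medium confidence. It concerns the exposure derivations and any display built on them, not the main growth and puberty summaries.

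**What to change.** In SAP 2.2 and 5.1.1, add a rule for a patient who has a study completion or discontinuation (SEC) page, no EOT page and no dose end date: set the dose end to the patient's own study completion visit, or last contact on study, and flag it as ongoing at exit. Keep the LPLV cut-off only for patients with no SEC page. State in SAP 2.2 that the EOT date is used where an EOT page exists, as in Scenario 2, and extend the cap to the daily-administration row of Table 5-1. A footnote to the exposure table should give the number of flagged patients.

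With the cap, exposure credited after exit is zero; the 2018 exit in the illustration returns to 8.00 years.

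The cost is a few sentences and one programming condition. Table 5-3 already uses a last-contact date on study, and the completion visit is a scheduled visit, so no new data are needed. The SAP amendment is marked as preceding final database lock, so this can be settled before lock.
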